- Primary endpoints: Human papillomavirus E6/E7 (HPV E6/E7)
- Secondary endpoints: NF-κB, p16INK4a, Rb, p53 and VEGF.

HPV E6/E7 mRNA testing has been demonstrated to be a useful tool in the diagnosis of cervical cancer prevention and will be the primary end-point for this aim. The primary objective for this study is to look at the association between curcumin and cervical disease. In vitro work shows that curcumin treatment inhibits the transcription of HPV E6/E7, thus restoring the expression of proteins such as p53 and that over expression of HPV E6/E7 is a good indicator of risk and progression to cancer. (Maher DM, 2011 Jan;50(1)). Collectively the vitro and our in vivo findings may show that curcumin should be considered an effective chemopreventive and therapeutic agent for cervical cancer prevention and treatment.

Aim2: To quantify levels of curcumin in the cervix of women in the curcumin treatment arm. The mean tissue concentration of curcumin in the cervix at each time point (baseline, 1,2,3,4, and 5 months) will be calculated. This secondary objective quantifies the pharmacologically active levels of curcumin recovered from cervical tissue, for information to be gathered on the levels of curcumin that is absorbed into the cervical tissue and thus eliciting a direct pharmacological effect.

Aim 3: To determine the association between curcumin and other known biomarkers of cervical disease. This exploratory aim seeks to use repeated-measures analyses, utilizing a linear mixed model for the curcumin group to assess the association between and each biomarker (NF-kB, p16INK4a, Rb, p53 and VEGF) and the concentration of curcumin at each time point (baseline, 1, 2, 3, 4, and 5 months).

The primary analysis will be conducted with a two sample two sided t-test to compare the each of the primary endpoints and secondary endpoints, between the two arms of the study, those on treatment (curcumin capsules) and those on the placebo, respectively. If normality cannot be assumed a Wilcoxon rank-sum test will be used instead. Chi-square test or Fisher's exact test will be used to compare categorical characteristics by treatment group.

In the secondary analyses, for the biomarker measurements, analyses of repeated measures methods are needed to properly account for the correlation between multiple observations from the same subject. Mixed-effects linear models will be employed to analyze such data while adjusting for covariates. Inference from such analyses will be limited by the small sample size of the study. However these data will provide important estimates of within-and between-subject variance that will be helpful for planning future studies. Repeated-measures analyses using mixed linear models will be performed for each biomarker outcome variable (E6/E7, p16INK4a, p53, Rb NF-kB, and VEGF). Each outcome will be analyzed with a means model with SAS Proc Mixed (version 9) providing separate estimates of the means by treatment group (curcumin and placebo) and time on study (baseline, 1,2,3,4, and 5 months). An unstructured variance-covariance form among the repeated measurements will be assumed for each outcome and estimates of the standard errors of parameters will be used to perform statistical tests and

construct 95% confidence intervals. The model-based means are unbiased with unbalanced and missing data, so long as the missing data are non- informative (missing at random). A p-value \leq 0.05 will be considered statistically significant for the main effects (treatment and time on study) and interaction term (treatment group by time on study) from the repeated measures analysis for each outcome. If there is a significant interaction effect then separate comparisons between the two treatment groups will be performed at each time point (baseline and 1,2,3,4, and 5 months). Results from these models will focus on the magnitude of the differences for each outcome. Data will be summarized using adjusted means plus 95% confidence intervals and observed differences plus 95% confidence intervals.

Additionally these biomarkers will also be quantified using immunohistochemistry methods. Immunostaining of p16 (NK4a) will be done and defined as moderate to strong diffuse or focal staining. This characterization of the staining pattern and intensity will allow one to evaluate the histological sample/biposy as having a negative, focal/patchy, or diffuse staining pattern. Generally, 100% of the low-grade and high-grade SIL's are positive for p16 staining and a strong diffuse staining with p16 suggests a high association with high-risk HPV associated lesions.

Acceptability Questionnaires: Descriptive statistics on subject and partner responses from the acceptability questionnaires will be reported.

Power and sample size calculation: The expression of E6/7 is the primary endpoint of the study and will be used in the power and sample size calculation with a two sample two sided t-test. In this study, we will enroll 20 patients in each of the two groups. Therefore, the group sample sizes of 20 in Curcumin group and 20 in placebo group will achieve at least 80% power at the significant level of 0.05 to detect a difference of a ratio of 1.536 or higher in the expression of E6/ between the two groups, assuming the coefficent of variation is 0.5.

SAFETY EVALUATION:

Adverse Events (AEs) and Serious Adverse Events (SAEs)

This investigational agent is studied under IND # 103496 and monitoring will be performed per previously agreed upon FDA guidance.

There may be some minor irritation from the intravaginal curcumin to the vaginal mucosa and staining of underwear. Other side effects which can happen include the upset stomach, diarrhea, burning sensation in the vagina, dizziness, insomnia, rash, pruritus generalized, and fever. The literature shows that over 13 subjects in United States and 151 subjects in India (10) have been studied with curcumin without any serious adverse effects.

Our phase I study has shown that curcumin is safe in dosage up to 2000mg.

Any patient intervention related adverse effects, an unanticipated problem, or reportable protocol deviation/ non-compliance will be reported to the Emory IRB office according to IRB P & P and to the FDA according to regulations.

Any serious adverse effects will be communicated by the principal investigator to the Emory IRB using the standard adverse event reporting forms.

SAEs will be defined per FDA standards and include those that result in death, are life threatening, result in a disability, cause for hospitalization, or to a congenital abnormality or birth effect. SAEs will be reported to the DSMC, IRB and FDA and manufacturer as required.

CLINCAL OUTCOMES AND MEASURES:

The table below gives the descriptions to be used to document findings during colposcopy.

| Colposcopic findings | | | | Presence | |
|----------------------|----------------------|----------------------|----------------------|----------|--------|
| | Grade 1 | Grade 2 | Grade 3 | | |
| | (Mild) | (Moderate) | (Severe) | Present | Absent |
| | Definitions provided | Definitions provided | Definitions provided | | |
| Peeling | If both the | If either the | If they involve | | |
| Ulcer | epithelium | epithelium | disruption of | | |
| Abrasion | and the blood | is | the | | |
| Ecchymosis | vessels are | superficially | epithelium; | | |
| Petechiae | intact | disrupted or | an area of the | | |
| Erythema | | the blood | epithelium | | |
| Edema | | vessels are | with bleeding | | |
| Grossly white | | disrupted | should be | | |
| lesion | | | considered | | |
| Sloughing | | | deeply disrupted | | |
| Laceration | | | | | |

Colposcopic findings (present or absent) will be summarized at each visit. Findings will be counted once, attribute to the time point/visit at which they were first detected, and described on the basis of their characteristics when they were first detected. The same criteria outlined in the WHO Update Colposcopy Manual to assess toxicity and mucosal damage to the cervix, vagina and perineum will be carefully followed.

DATA AND SAFETY MONITORING PLAN (DSMP):

The primary risk to this study relates to potential complications with vaginal sampling, vaginal mucosa irritation and colposcopy with targeted cervical biopsies/LEEP. [name] will monitor subject safety and respond to occurrences if AEs/SAEs in a timely manner.

The Data and Safety Monitoring Committee (DSMC) of the Winship Cancer Institute will provide oversight for the conduct of this study. The DSMC functions independently within Winship Cancer Institute to conduct internal monitoring functions to ensure that research being conducted by Winship Cancer Institute Investigators produces high quality scientific data in a manner consistent with good clinical practice (GCP) and appropriate regulations that govern clinical research. Depending on the risk level of the protocol, the DSMC review may occur every 6 months or annually.

For this study: deemed Moderate Risk, initial study monitoring will occur within 1 year from the date of the first subject accrued, with 2 of the first 5 subjects being reviewed. Subsequent monitoring will occur in routine intervals per the Winship Data and Safety Monitoring Plan (DSMP).

The DSMC will review pertinent aspects of the study to assess subject safety, compliance with the protocol, data collection, and risk-benefit ratio. Specifically, the Winship Cancer Institute Internal Monitors assigned to the DSMC may verify informed consent, eligibility, data entry, accuracy and availability of source documents, AEs/SAEs, and essential regulatory documents.

Following the monitoring review, monitors will provide a preliminary report of monitoring findings to the PI and other pertinent individuals involved in the conduct of the study. The PI is required to address and

respond to all the deficiencies noted in the preliminary report. Prior to the completion of the final summary report, monitors will discuss the preliminary report responses with the PI and other team members (when appropriate). A final monitoring summary report will then be prepared by the monitor.

Final DSMC review will include the final monitoring summary report with corresponding PI response, submitted CAPA (when applicable), PI Summary statement, and available aggregate toxicity and safety data. The DSMC will render a recommendation and rating based on the overall trial conduct. The PI is responsible for ensuring that instances of egregious data insufficiencies are reported to the IRB. Continuing Review submissions will include the DSMC recommendation letter. Should any revisions be made to the protocol-specific monitoring plan after initial DSMC approval, the PI will be responsible for notifying the DSMC of such changes. The Committee reserves the right to conduct additional audits if necessary.

Adverse events observed or reported by subjects will be monitored by the physicians from this study and will also be reviewed by professional colleagues within infectious disease, GynOb and pathology. Subjects will be given the contact phone numbers to call if they experience any problems (increased discharge, vulvovaginal irritation). They will be followed routinely, every 4 weeks by the physicians using colposcopy, biopsy and cytology to identify any high risk features or progression of the disease.

Stopping/Pausing Rules

| Symptom or AE | Toxicity Grade | Duration | Criteria | Action required |
|----------------------|--|----------|---|---|
| Colposcopic findings | Grade II or greater Grade I not resolved in 2 weeks | • N/A | One participant report the product-related symptoms at a specified grade | Prompt notification of DSMB, IRB, NIH, FDA and CTRC. All product application is help until further notice, follow up and resolution |

This study does involve intervention with a product and the protocol does require the collection of sensitive and confidential information, biological samples (genital tract), physical examination, colposcopy and pharmacological intervention (curcumin). As with any study that includes these procedures there may be side effects from the study procedures that are not known at this time. However, for those common risks and discomforts expected in this study they are outlined in the consent forms, and also listed below with the methods to minimize any associated risk:

1: Physical exams

Participants may feel some minor physical discomfort. This should be minor and will go away quickly. All physical tests and examinations will be performed by a trained and experienced health care practitioner.

2: Biologic Sample collection (genital tract sample collection) and colposcopy with biopsy:

For genital tract sample collections, participants may feel some minor physical discomforts and experience spotting or bleeding from cervical biopsy collections.

- 3: As this study involves pharmacological intervention subjects will be administered a pregnancy test will be administered by an experienced health care practitioner before enrollment and at each study visit during the course of the study.
- 4. This study requires intravaginal placement the capsules (curcumin or placebo). Pill diaries will be given and monitored at each visit. Subjects will also be contacted twice a week to ensure adherence and be given the ability to report any adverse events/side effects like vaginal discharge and vulvo-vaginal irritation.
- 5. Subjects will be informed of potential risks and sign a written informed consent for participation. Subjects will be asked to agree to the use of reliable birth control: Combined oral contraceptive pill (OCP), Long Lasting Reversible Contraceptive (LARCP), Bi-Lateral Tubal Ligation (BLT) and Depo-Provera Shot/Birth control shot.
- 5b. Partner notification letters will indicate the need for condom use and the risk of discoloring and/or irritation if a condom is not used when having vaginal sex with an enrolled female participant.
- 6. Patient confidentiality will be protected by identifying study subjects and samples by code number. Study records will be kept on password protected computers or in a locked office. Only the study coordinators, Nurse Practitioners, Interviewers, and PIs will have access to de-identified information. Collaborators and staff outside Emory listed on the study will not have access to HIPAA protected information.
- 7. Careful training of study staff on ethical research practices, informed consent, and confidentiality. The Investigative team will meet on a bi-weekly basis during subject enrollment and monthly to review AEs and any SAEs, discuss recruitment, drop-outs/withdrawals and any protocol problems.
- 8. Summaries of adverse events (Grades 3 or 4) and other targeted AEs will be reviewed regularly by study investigators. The standard Emory IRB and FDA reporting guidelines for adverse events will be followed.

Written IND safety reports will be submitted to the FDA for serious, unexpected suspected adverse reactions within 15 calendar days of learning of its occurrence. If the event is fatal or is deemed to be life threatening, the report will be made within 7 calendar days. The IND sponsor will also make an assessment of whether the event constitutes an unanticipated problem posing risks to subjects or others (UP). This assessment will be provided to the Emory University IRB, which, in turn will make a final determination. If the Emory IRB determines an event is a UP it will notify the appropriate regulatory agencies and institutional officials.

Standard procedures will be followed to ensure the safety and security of subject information. Throughout this process, patient confidentiality will be maintained via de-identification of patient information. Electronic information will be stored only on password protected media, and any required paper documentation will be kept in a locked and secured location.

CLINICALTRIALS.GOV REGISTRATION

We will ensure to submit the required clinical trial information prior to enrollment of the first participant for this study.

HUMAN SUBJECTS

I. 1 Responsibilities of the Investigator

In implementing this protocol, the investigators will adhere to the basic principles of "Good Clinical Practice" as outlined in CFR 312, subpart D, "Responsibilities of Sponsors and Investigators," CFR 21, part 50 and CFR 21, part 56 and Section 4 of ICH Harmonized Tripartite Guideline for GCP.

II. IRB Review and Informed Consent

This protocol and the informed consent document and any subsequent modifications will be reviewed and approved by the Emory University IRB. A signed and dated, Emory IRB-approved consent form will be obtained from the subject. The consent form will describe the purpose of the study, the procedures to be followed, and the risks and benefits of participation. A signed copy of the consent form will be given to the subject, parent, or legal guardian, and this will be documented in the subject's record.

III. 8.3 Subject Confidentiality

All laboratory specimens, evaluation forms, reports, and other records that leave the site will be identified only by coded number to maintain subject confidentiality. All records will be kept locked. All computer entry and networking programs will be done with coded numbers only. Clinical information will not be released without written permission of the subject, except as necessary for monitoring by IRB or the OHRP.

IV. 8.4 Study Discontinuation

A study participant may elect to discontinue participation in the study at any time. The study may be discontinued at any time by the IRB, the OHRP, or other government agencies as part of their duties to ensure that research subjects are protected.

BIOHAZARD CONTAINMENT

As the transmission of HIV and other blood-borne pathogens can occur through contact with contaminated needles, blood, and blood products, appropriate blood and secretion precautions will be employed by all personnel in the drawing of blood and handling of all specimens for this study, as currently recommended by the Centers for Disease Control and Prevention and the National Institutes of Health.

All infectious specimens will be transported using packaging mandated in the Code of Federal Regulations, 42 CFR Part 72.

REFERENCES

- Center for Disease Control and Prevention. Cervical Cancer Statistics. 2011.

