Although clinical studies have shown that curcumin is safe and well tolerated with no significant toxicity and an acceptable blood chemistry profile, its use is limited by its low systemic bioavailability (9, 10, 14, 15, 17). To circumvent this problem, we administered curcumin capsules through an intravaginal approach and tested safety, tolerability and acquired pharmacokinetic data. We found no severe adverse events or dose limiting toxicities during our phase I trial of 13 subjects treated daily for 14 days with intravaginal curcumin (appendix 1). Three subjects (1 taking 1000 mg dose, 2 taking 1500 mg dose) completed 13 of the 14 days, with the reason for non-compliance being they chose not to finish. In addition, curcumin and curcumin conjugates were not measurable in the serum, and detectable concentrations were not observed in the urine of study participants (presented at Eurogin 2011). With a low side effect profile, easy application, and low cost, this potentially therapeutic herb can be sustainable in low resource countries. We are also supported by a recent study from India conducted by Basu(10) et al 2013. Their study clearly demonstrated that intravaginal curcumin is safe and tolerable. The main reason for the

discontinuation of the drug was vulvovaginal irritation and itching. This application explores the effect of topical application of curcumin as a potential chemoprevention agent in the suppression of cervicovaginal HPV infection and subsequent risk for cancer of the cervix. IND #103496 is in place to proceed with this study.

SPECIFIC AIMS

This application explores the effect of curcumin, a known chemotherapeutic agent as a potential medical treatment in HIV uninfected and infected women (without AIDS defining illness) with high grade squamous intraepithelial lesions (HSIL) of the cervix. We plan to address our specific aims by conducting a pilot two-arm study in which women will be randomized to 2000 mg of intravaginal curcumin versus placebo weekly for 12 weeks.

The specific hypothesis of this phase II study is that intravaginal curcumin will decrease expression of HPV oncogenic biomarkers associated with cervical cancer and this will correlate with the levels of curcumin detectable in the cervical tissue.

Specific Aim 1 (Primary Objective):

Determine the association between intravaginal curcumin on known HPV-related molecular target HPV E6/E7 mRNA expression within HSIL lesions of the cervix in HIV uninfected and infected women.

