
Rationale:

The HPV E6/E7 oncoproteins have significant roles in malignant transformation and are consistently expressed in malignant cervical tissue. Increasing levels of E6 and E7 expression cause genetic instability, and implies a risk for cellular changes, which results in a selective growth advantage (31, 34-37). The APTIMA® HPV Assay that we will be utilizing in our studies detects full-length HPV E6/E7 mRNA for HPV types 16, 18, 31, 33, 35, 39, 45, 51, 52, 56, 58, 59, 66, and 68 and correlates very well with integrated HPV, which in turn correlates with full-length HPV E6/E7 protein levels (38).

All methodologies for evaluating the expression and function of HPV E6/E7 are ongoing in the laboratory of the co-investigator ([name]) and are described in referenced publications (27-34). The expression of HPV E6/E7 proteins will be assessed by the APTIMA* HPV Assay using liquid-based cytology specimens.

Specific Aim 2 (Secondary Objective):

To quantify levels of curcumin in the cervix of women in the curcumin treatment arm.

Rationale:

To date, there are no published data on the tissue penetration of curcumin in vivo. This will establish the level of curcumin penetration in cervical tissue as well as the cumulative effect of weekly curcumin over time. This study will establish the baseline which is crucial in designing further curcumin intervention studies. The methodology of curcumin measurement for this study is well documented in Subhashini et al (16).

Specific Aim 3 (Exploratory Aim):

To determine the association between curcumin and other known biomarkers of cervical disease and its effect on the vaginal microbiome.

Rationale:

To determine the most relevant duration for curcumin treatment, as well as identify additional biomarkers that are regulated with the pharmacological activity of curcumin, we will measure mRNAand/or protein expression levels of p16INK4a, p53, Rb, VEGF and NF-κB in cervical biopsy specimens. A combination of immuno-histochemical methods and other molecular assays (RT-PCR, ELISA, TransAM NF-κB DNA binding ELISA) to determine mRNA levels and protein levels on transcription factor binding activity will also be done.

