A speculum will be inserted into the vagina to visualize the cervix. A sample of cells from the outer opening of the cervix is collected with a plastic cytobroom/endocervical brush which is rotated in the central opening of the cervix. The cells are placed on in liquid media (SurePath) and ThinPrep (HPV) and taken to the laboratory to be checked for abnormalities /cervical disease and HPV.

1.3 Follow up:

Subjects will be contacted within 48 hours after the start of the medication to inquire on any issues affecting your adherence to the study medication after the baseline visit.

Subjects will receive a call twice a week from week 4 through week 16 to inquire on any issues affecting your adherence to the study medication.

All women will be contacted by telephone to discuss all cytology and histology results and Cytology and histology results will be available for all study participants PCP if a medical release waiver is signed by the subject. We will be following these subjects every month with colposcopy which is more than sufficient to capture any women at risk for progression and they will be referred to treatment is progression of disease occurs.

- 2 Laboratory Evaluations
- 2.1 Pap and HPV testing will be performed by Grady pathology lab.
- 2.2 The APTIMA® HPV Assay (HPV viral load quantitative/ Detection of HPV mRNA Levels)

The Aptima HPV assay offers a unique screening approach by targeting high-risk human papillomavirus (HPV) mRNA from the E6/E7 oncogenes. The Aptima HPV assay offers the same excellent sensitivity and improved specificity as compared to DNA-based tests. The expression and function of HPV E6/E7 a will be conducted in the lab of [name].

STATISTICAL ANALYSIS:

Aim1: To determine the association between intravaginal curcumin on known HPV-related molecular target HPV E6/E7 mRNA expression within HSIL lesions of the cervix in HIV uninfected and infected women. Biomarkers are known to be differentially regulated in cervical disease. Current literature shows that HPV E6/E7 mRNA, NF-kB, p16INK4a and VEGF levels are up-regulated, whereas p53 levels are down-regulated in cervical disease. Biomarker outcome, defined as the level of mRNA and/or protein in the samples collected, will be summarized with standard descriptive statistics and represented graphically with displays such as box plots by treatment group. For this study the biomarkers whose levels will be quantified are as follows:

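### Aim 1 claims E6/E7 expression within the lesion, but the only specimen named for it is cytology that is not lesion-directed, and the curcumin-concentration model omits E6/E7

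*Combined protocol and SAP*

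**What the plan says.** **Objective.** Specific Aim 1, repeated under Aim 1 of Statistical Analysis, sets the target as "HPV E6/E7 mRNA expression within HSIL lesions of the cervix". The Summary places E6/E7 first in a list of targets to be studied inside HSIL lesions.

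**Specimen for E6/E7.** The Rationale under Specific Aim 1 has E6/E7 assessed with the APTIMA assay "using liquid-based cytology specimens". Section 1.2 (Pap with Cervical swabs) describes the collection: "A sample of cells from the outer opening of the cervix is collected with a plastic cytobroom/endocervical brush", with the brush turned in the central opening. Nothing directs it to a lesion seen at colposcopy.

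**Specimen for the other markers.** The Rationale under Specific Aim 3 assigns "p16INK4a, p53, Rb, VEGF and NF-κB in cervical biopsy specimens". E6/E7 is not in that list.

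**Relation to tissue curcumin.** The Summary says the study will examine whether expression of the molecular targets is associated with curcumin concentration in tissue. The hypothesis in Specific Aims says the fall in oncogenic biomarkers will correlate with tissue curcumin. The model meant to do this (Statistical Analysis, Aim 3) is a linear mixed model in the curcumin arm for NF-κB, p16INK4a, Rb, p53 and VEGF only.

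**The concern.** The question asked and the specimen named to answer it are different. A brush sample mixes cells from the lesion with cells from elsewhere on the cervix, in proportions that may vary by woman and visit. A difference between arms could reflect expression per lesion cell, the number of lesion cells picked up, or both. Signal from outside the lesion could also hide a real lesion effect. The protocol does not say how a cytology result is to be read as a lesion result.

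What is at stake is the conclusion the trial may draw from its primary endpoint. This pilot is meant to inform a larger phase 2 trial. A reader of the report would take Aim 1 at its word and assume that expression in the lesion had been measured.

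The second gap is separate. The exposure-response link is half of the stated hypothesis, and as written it is never tested for the primary marker.

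**Working it through.** **1. The plan's own figure.** Inputs from Power and sample size calculation: 20 per arm, two-sided 0.05, ratio 1.536, coefficient of variation 0.5. On the log scale:
- σ = √ln(1 + 0.5²) = √ln 1.25 = 0.4724
- δ = ln 1.536 = 0.4292
- noncentrality = 0.4292 / (0.4724 × √(2/20)) = 2.873

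With 38 degrees of freedom the exact t-test power is 79.95% (normal approximation 81.9%). The stated 80% is reproduced. That paragraph does not say to which specimen the ratio and the coefficient of variation apply.

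**2. Is E6/E7 in tissue planned anywhere?**

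| Place | What it says | E6/E7 in tissue named? | Excluded? |
|---|---|---|---|
| Aim 1, Rationale | assay on liquid-based cytology | no | no |
| Aim 3, Rationale | five other markers in biopsies | no | no |
| Research Design and Methods | cytology and biopsies both serve aims 1 to 3 | no | no |
| Endpoints | LEEP tissue tested for unspecified biomarkers | no | no |
| Samples | biopsies split between pathology with p16 and storage | no | no |
| Statistical Analysis, Aim 1 | outcome is the level in whatever samples are collected | no | no |
| Statistical Analysis, immunohistochemistry paragraph | biomarkers also quantified by staining; only p16 described | no | no |

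Cytology is the only specimen named, and tissue is left open.

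**3. Is E6/E7 related to tissue curcumin anywhere?** The Aim 3 concentration model lists five markers without it. The repeated-measures model under the secondary analyses does include E6/E7, but its factors are treatment group and time, not concentration. So no planned model relates the primary marker to tissue curcumin.

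**4. What dilution would do, under an assumption.** Let f be the share of the placebo-arm cytology signal that comes from the lesion. Assume that signal from elsewhere does not respond to treatment, that the coefficient of variation stays 0.5, and that the true lesion ratio is 1.536. The cytology ratio is then 1 / (f/1.536 + 1 − f). The documents give no value for f, so the range is shown only to indicate how the answer depends on it.

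| f (assumed) | Cytology ratio | Exact power, 20 per arm |
|---|---|---|
| 1.0 | 1.54 | 80% |
| 0.9 | 1.46 | 69% |
| 0.75 | 1.35 | 51% |
| 0.5 | 1.21 | 24% |
| 0.25 | 1.10 | 9% |

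If 1.536 was meant as the ratio in cytology, the power is as stated for any f, and f bears only on interpretation.

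**The case against.** The strongest reply has four parts.

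- **Tissue measurement is not ruled out.** The table above bears this out. A reader might infer that E6/E7 is measured only in cytology. The documents do not go that far: cytology is the only specimen named, and the assignment is otherwise unclear.
- **The cytology comparison is valid.** All participants are to have biopsy-proven HSIL and are randomised. The Aim 1 Rationale also supports the assay by its reported correlation with integrated HPV and E6/E7 protein. A reader might infer that the result says nothing about the lesion. That is too strong: it is indirect evidence. The Rationale argues for the assay, however, and not for reading a brush sample as a lesion sample.
- **Biopsies are not a clean contrast.** The four additional punches, one per quadrant, are not lesion-directed either. This stands, and it means a lesion-level claim would need its tissue specified.
- **Different specimens do not prevent a correlation.** Cytology and biopsies are taken at the same visits, so cytology E6/E7 can be related to tissue curcumin. This stands too. The gap is that E6/E7 is missing from the model.

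A reader might also infer that a fall in E6/E7 would be an artefact of shedding or repeat biopsy. Repeat biopsies follow the same schedule in both arms. Differential irritation is possible, since Safety Evaluation anticipates some from curcumin, but the documents give no figure for its effect on the cells collected.

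**Conclusion.** The point holds in two parts. First, the primary objective is worded at lesion level, while the only specimen named for its endpoint is not lesion-directed. The primary comparison supports a conclusion about E6/E7 mRNA in exfoliated cervical cells and bears on the lesion only indirectly. Second, the promised relation between E6/E7 and tissue curcumin has no planned analysis.

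The first part has no numerical size that the documents can supply. The stated sample size and power reproduce and are not challenged. A reader might infer from the dilution table that the trial is underpowered. That is not supported, because f is unknown and the effect size is not tied to a specimen.

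The conclusion rests on reading the Aim 1 Rationale as the operative assignment of specimen. If the investigators already intend tissue E6/E7, the remaining defect is that the protocol does not say so.

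**What to change.** 1. Restate the primary objective (Summary, Specific Aim 1, and Aim 1 of Statistical Analysis) and the permitted conclusion as E6/E7 mRNA in cervical cytology specimens. This costs wording only.
2. Add E6/E7, from cytology taken at the same visits, to the Aim 3 mixed model against tissue curcumin concentration, and describe the result as an association across two specimen types. This costs one more model, with no extra sample or visit.
3. If a lesion-level claim is kept, name the lesion-directed biopsy or LEEP tissue on which E6/E7 will be measured and report that analysis as supportive. This is not free: the named assay covers 14 HPV types, so tissue measurement needs a method that copes with them, and it depends on what tissue remains after the split described under Samples.

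Normalising the cytology value to cell content should not be offered as a substitute. It adjusts for how many cells were collected, not for what share came from the lesion.
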